9.3. Analysis sets (amended 16 December 2022)

Table 18 Analysis sets

Analysis set	Description
Enrolled set*	Participants who agreed to participate in a clinical study after completion of the informed consent process.
Exposed set (ES)	All participants who received a study intervention. Analysis per group is based on the study intervention administered.
Per-Protocol set (PPS)	All eligible participants who received at least one study intervention as per-protocol in the Control group and all study interventions in the Co-Ad group , had immunogenicity results pre- and post-dose for at least one antigen , complied with blood draw intervals (refer to Table 3 and Table 4) and contribution of participants to PPS at specific timepoint will be defined by timepoint, without intercurrent medical conditions that may interfere with immunogenicity and without prohibited concomitant medication/vaccination.

* All participants enrolled and included in the database will be part of the enrolled set.

9.3.1. Criteria for elimination from analysis

If the participant meets one of the criteria mentioned in the Sections [7.1.1](#) (contraindication to subsequent vaccination) or [5.2.1](#) (medical conditions) or [5.2.2](#) (concomitant therapy), he/she may be eliminated from per-protocol analysis.

In case of unplanned administration of any medication mentioned in Section [5.2.2](#) during the study, this will be considered as a protocol deviation and the participant may be eliminated from the PPS.

Participants may be eliminated from the PPS for immunogenicity if, during the study, they incur a condition that has the capability of altering their immune response (intercurrent medical condition) or are confirmed to have an alteration of their initial immune status. Refer to [Glossary of terms](#) for the definition of intercurrent medical conditions.

9.4. Statistical analyses

The Statistical Analysis Plan (SAP) will be developed and finalized before first subject first visit (FSFV). This section is a summary of the planned statistical analyses of the primary and secondary endpoints. Supportive analyses, safety and demography summaries will be described in the SAP.

9.4.1. Primary endpoints (amended 16 December 2022)

The **primary** endpoints are described in Section 3. The confirmatory analyses of non-inferiority will be based on the Per-Protocol (PP) set.

- Method for non-inferiority of RSVPreF3 OA investigational vaccine in terms of RSV-A neutralization antibody GMT ratio at 1 month after the RSVPreF3 OA investigational vaccine dose (i.e. at Day 31 for the Co-Ad group and at Day 61 for the Control group):

The 2-sided 95% confidence interval (CI) for group GMT ratio between RSVPreF3 OA investigational vaccine administered alone (Control group) over RSVPreF3 OA investigational vaccine when co-administered with the FLU vaccine (Co-Ad group) will be derived from an ANCOVA model* on \log_{10} transformed titer.

- Method for non-inferiority of FLU vaccine in terms of HI GMT ratio for each of the FLU vaccine strains at 1 month after the FLU vaccine (i.e. at Day 31 for both groups):

The 2-sided 95% CI for group GMT ratio between FLU vaccine administered alone (Control group) over RSVPreF3 OA investigational vaccine when co-administered with the FLU vaccine (Co-Ad group) will be derived from an ANCOVA model* on \log_{10} transformed titer.

- Method for non-inferiority of RSVPreF3 OA investigational vaccine in terms of RSV-B neutralization antibody GMT ratio at 1 month after the RSVPreF3 OA investigational vaccine dose (i.e. at Day 31 for the Co-Ad group and at Day 61 for the Control group).*

The 2-sided 95% CI for group GMT ratio between RSVPreF3 OA investigational vaccine administered alone (Control group) over RSVPreF3 OA investigational vaccine when co-administered with the FLU vaccine (Co-Ad group) will be derived from an ANCOVA model on \log_{10} transformed titer.*

*The model will include the treatment group and age category (age at vaccination: 65-69, 70-79 or ≥ 80 years) as fixed effects, and the pre-dose \log_{10} -transformed titer as covariate. Missing data will not be replaced. Titers below the assay cut-off will be replaced by half the assay cut-off, titers above the upper limit of quantification (ULOQ) will be replaced by the ULOQ.

9.4.1.1. Success criteria for non-inferiority and testing sequence:

The following testing sequence will be used:

1st sequence:

- *The upper limit of the 2-sided 95% CI of the GMT ratio (Control group divided by Co-Ad group) for RSV-A neutralization antibodies is ≤ 1.5 .*

AND

- *The upper limit of the 2-sided 95% CI of the GMT ratio (Control group divided by Co-Ad group) for each of the FLU vaccine strains are ≤ 1.5 .*

2nd sequence:

- *The upper limit of the 2-sided 95% CI of the GMT ratio (Control group divided by Co-Ad group) for RSV-B neutralization antibodies is ≤ 1.5 .*

Testing will progress in the 2nd sequence only if the 1st sequence is a success, so that no further adjustment of alpha is required.

9.4.2. Secondary endpoints

- Method for evaluation of non-inferiority of FLU vaccine in terms of HI seroconversion rate for each of the FLU vaccine strains at 1 month after the FLU vaccine (i.e. at Day 31 for both groups):
 - The 2-sided 95% CI on group difference in seroconversion rate (Control group minus Co-Ad group) will be computed based on the method of Miettinen and Nurminen [[Miettinen](#), 1985].
 - Reference criteria for evaluation of non-inferiority: The upper limit of the 2-sided 95% CI on the group difference (Control group minus Co-Ad group) in seroconversion rate is $\leq 10\%$ for anti-HI antibodies.
- The other secondary endpoints are described in Section 3. Descriptive analyses of demography, immunogenicity and safety will be detailed in the SAP.

Table 19 Definitions of seroconversion rate, seroprotection rate and mean geometric increase

Abbreviation/term	Definition
HI SCR/ seroconversion rate	The percentage of vaccinees who have either a HI pre-dose titer $< 1:10$ and a post-dose titer $\geq 1:40$ or a pre-dose titer $\geq 1:10$ and at least a four-fold increase in post-dose titer.
HI SPR/ seroprotection rate	The percentage of vaccinees with a serum HI titer $\geq 1:40$ that usually is accepted as indicating protection.
MGI/ mean geometric increase	The geometric mean of the within participant ratios of the post-dose titer over the pre-dose titer.

- Additionally, the CBER and CHMP criteria for HI SPR and SCR will be assessed as follows:

CBER's criteria:

- The lower limit (LL) of the 95% CI for SCR should be $\geq 30\%$ in participants ≥ 65 YOA.
- The LL of the 95% CI for SPR should be $\geq 60\%$ in participants ≥ 65 YOA.

CHMP's criteria:

At least one of the 3 following criteria should be met:

- the point estimates of SPR $>60\%$, SCR $>30\%$, and MGI >2.0 for elderly ≥ 60 YOA for each of the antigen strains.

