9.2. Sample size determination (amended 16 December 2022)

The target enrolment will be 1028 participants (514 in the group receiving the RSVPreF3 OA investigational vaccine co-administered with the FLU vaccine (Co-Ad group) and 514 in the Control group where RSVPreF3 OA investigational vaccine and FLU vaccine are administered staggered) to obtain at least 924 evaluable participants (462 in the Co-Ad group and 462 in Control group) for the evaluation of the ***primary objectives***, assuming that approximately 10% of the enrolled participants will not be evaluable.

Table 16 Overall power to demonstrate primary objectives: non-inferiority of the immunogenicity of RSVPreF3 OA investigational vaccine when co-administered with FLU vaccine as compared to when administered alone- assuming 462 participants are available in each group.

Endpoint	Standard deviation of \log_{10} concentration	Reference ratio	Non-inferiority margin	Type II error	Power
RSV-A Non-inferiority* (1-sided test with alpha = 2.5%)					
GMTs RSV-A neutralization antibody	0.45	1.05	1.5	0.1%	99.9%
FLU Non-inferiority* (1-sided test with alpha=2.5%)					
GMTs HI H1N1 strain	0.6	1.05	1.5	2.5%	97.5%
GMTs HI H3N2 strain	0.6	1.05	1.5	2.5%	97.5%
GMTs HI B/Yamagata	0.6	1.05	1.5	2.5%	97.5%
GMTs HI B/Victoria strain	0.6	1.05	1.5	2.5%	97.5%
RSV-B Non-inferiority* (1-sided test with alpha = 2.5%)					
GMTs RSV-B neutralization antibody	0.45	1.05	1.5	0.1%	99.9%
Global Type II error to show non-inferiority				~10.0%	
Global power					~90.0%

* Pass 2019 alpha = 2.5%, Two-Sample T-Tests for Non-Inferiority Assuming Equal Variance and Equal mean

For RSV: non-inferiority limit = 0.176 ($=\log_{10}[1.5]$).

For each Flu vaccine strain: non-inferiority limit = 0.176 ($=\log_{10}[1.5]$).

Reference Ratio= 0.0212 ($=\log_{10}[1.05]$)

Considering a slight interference of 1.05 in true GMTs in both groups with a common population standard error of 0.45 for the RSV-A **and RSV-B neutralization antibodies** and 0.6 for each of the FLU strains in \log_{10} transformed concentration, the study has at least 90.0% power to meet the ***primary objectives***.

Nominal powers to evaluate secondary objective

The nominal power to evaluate the non-inferiority on seroconversion rate for each of the FLU strains is above 86%, depending on the plausible rates.

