Table 17 Evaluation of non-inferiority in terms of HI antibody SCR when the FLU vaccine is co-administered with the RSVPreF3 OA investigational vaccine as compared to FLU when administered alone assuming 462 participants are available in each group for a range of plausible SCRs.

N evaluable participants per group	Threshold	Plausible rates in Control group**	Type II error	Nominal power
FLU vaccine: Non-inferiority* in terms of SCR				
462	10%	70%	8.7%	91.3%
462	10%	50%	13.9%	86.1%
462	10%	35%	11.0%	89.0%
462	10%	25%	6.1%	93.9%

SCR: Seroconversion Rate.

*Pass 2019 alpha = 2.5%, for SCR – Non-inferiority: Proportions – Two independent Proportions – Non-Inferiority Tests for the Difference Between Two Proportions.

** SCR observed in the Control group in Zoster-004 study range from 35.3% to 60.9%.

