4.3.1.1. Between groups assessment

- The asymptotic standardized 95% CI for the difference in seroconversion rate (Control group minus Co-Ad group) will be computed at 1 month after the FLU vaccine (i.e. at Day 31 [Visit 2] for both groups).

Reference criteria for evaluation of non-inferiority:

The upper limit of the 2-sided 95% CI on the group difference (Control group minus Co-Ad group) in seroconversion rate is $\leq 10\%$ for anti-HI antibodies.

The between groups analysis of secondary endpoints presented in this section will be descriptive with the aim to characterize the difference in immunogenicity between groups. These descriptive analysis should be interpreted with caution considering that there is no adjustment for multiplicity for these comparisons.

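### The seroconversion-rate comparison leaves out the Day 1 HI titer, which costs some precision on a descriptive secondary endpoint

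*Protocol*

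**What the plan says.** Protocol 9.4.2 states: "The 2-sided 95% CI on group difference in seroconversion rate (Control group minus Co-Ad group) will be computed". The method named there is Miettinen-Nurminen. The upper limit is compared with a 10-point reference limit, strain by strain. SAP 4.3.1.1 puts it as follows: "The asymptotic standardized 95% CI for the difference in seroconversion rate (Control group minus Co-Ad group) will be computed" at Day 31. SAP 4.1.1 confirms Miettinen-Nurminen for all differences in proportions. No stratum or covariate appears in any of these places, and the only sensitivity model (SAP 4.2.3) concerns the GMTs.

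Protocol Table 19 makes seroconversion depend on the pre-dose titer. A participant below 1:10 must reach 1:40, and anyone else needs a four-fold rise. Protocol Table 11 has Day 1 HI measured for every strain in all participants of both groups. Minimization (Protocol 6.3.3) balances age category and center only.

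The HI GMT ratio is handled differently. In Protocol 9.4.1, "The model will include the treatment group and age category", and the log10 pre-dose titer is added as covariate. SAP 4.2.2 agrees.

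On power, Protocol 9.2 says "The nominal power to evaluate the non-inferiority on seroconversion rate for each of the FLU strains is above 86" percent, with Table 17 giving 91.3, 86.1, 89.0 and 93.9% at control SCRs of 70, 50, 35 and 25%. SAP 4.3.1.1 describes the between-group secondary analyses as descriptive and without multiplicity adjustment.

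**The concern.** The endpoint is built from a baseline value that the trial collects in everyone and already uses in the GMT model for the same strain, yet the SCR comparison does not use it. If Day 1 titer predicts seroconversion, part of the variance of the SCR difference is removable and the interval is wider than it needs to be. The stated power is also lower here than for the GMTs: 86.1% per strain at SCR 50%, against 97.5% per strain in Protocol Table 16.

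The stakes are modest. The comparison has its own non-inferiority objective, reference limit and power table, so readers will treat each strain as having met or missed 10 points. An adjusted GMT ratio and a crude SCR difference for the same strain could also diverge slightly because only one of them accounts for baseline.

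**Working it through.** **Inputs from the documents.** 462 evaluable per group; margin 10 points; one-sided alpha 2.5%; control SCRs and powers from Protocol Table 17; SD of log10 HI titer 0.6 (Protocol 9.2); two-fold dilutions from 1:10 (Protocol 10.2).

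**Inputs not in the documents.** The true SCR difference (zero reproduces the table), the pre-dose titer distribution, and the pre/post correlation. R² below is the share of seroconversion variance explained by Day 1 titer. It is assumed.

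**Step 1: reproduce Table 17.** Power = Φ(0.10/SE − 1.96), with SE = √(2p(1−p)/462). At p = 0.50, SE = 0.0329 and power = Φ(3.04 − 1.96) = 86.0%. All four rows agree with the plan:

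| Control SCR | Plan | Unpooled | Score variance |
|---|---|---|---|
| 70% | 91.3 | 91.3 | 91.3 |
| 50% | 86.1 | 86.0 | 86.2 |
| 35% | 89.0 | 89.0 | 89.1 |
| 25% | 93.9 | 93.9 | 93.9 |

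**Step 2: use the baseline titer.** Multiply the variance by (1 − R²). At p = 0.50 and R² = 0.10, SE = 0.0329 × √0.90 = 0.0312 and power = Φ(3.20 − 1.96) = 89.3%. Power (gain in points):

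| Control SCR | R² = 0.05 | R² = 0.10 | R² = 0.15 |
|---|---|---|---|
| 70% | 92.5 (1.2) | 93.8 (2.5) | 94.9 (3.6) |
| 50% | 87.7 (1.7) | 89.3 (3.3) | 90.9 (4.9) |
| 35% | 90.5 (1.5) | 91.9 (2.9) | 93.3 (4.3) |
| 25% | 95.0 (1.1) | 95.9 (2.0) | 96.8 (2.9) |

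**Step 3: what R² could be.** A grid of 96 scenarios took a pre-dose log10 mean of 1.3 or 1.7, pre-dose SD 0.4 to 0.6, correlation 0.3 to 0.8 and the plan's SD of 0.6 post-dose, with each titer level as its own category. R² ran from about 0.01 to 0.19 and the gain from 0.1 to 5.7 points. At SCR 25% the gain was 0.1 to 2.3 points, under 2 in 23 of 24 scenarios.

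**Step 4: simulate the stratified comparison.** Strata were <10, 10–<40, 40–<160 and ≥160, with Mantel-Haenszel weights and a Wald variance. The pre-dose SD was 0.6 and the correlation 0.3 to 0.7. Power rose in all 30 scenarios of one run, by 0.7 to 4.9 points. It also rose in all 18 scenarios of a separate run at SCR 35, 50 and 61%, by 1.2 to 5.2 points. Examples at SCR 50%:

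| Pre-dose mean | Correlation | Crude | Stratified |
|---|---|---|---|
| 1.7 | 0.3 | 85.9% | 90.9% |
| 1.7 | 0.5 | 85.4% | 88.8% |
| 1.7 | 0.7 | 85.9% | 87.5% |
| 1.3 | 0.5 | 86.4% | 88.4% |

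Simulation error on one power is about 0.5 points (√(0.86 × 0.14/4000)). Type I error at the 10-point limit was about 2.2 to 2.8% stratified and 2.1 to 2.8% crude.

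**Step 5: categories or a linear term.** The relation need not be monotone, because the rule changes at 1:10. With pre-dose mean 1.3, correlation 0.7 and overall SCR 50%, simulated SCR was 37% below 1:10, 65% at 10–<40, 49% at 40–<160 and 31% at ≥160. In that setting a linear titer term explained 0.0% of the variance, and titer levels as categories explained 6.7%.

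**Step 6: chance imbalance.** One SD of baseline imbalance moves the crude difference by √R² × SE. At SCR 50% this is √0.10 × 3.29 = 1.0 point, or √0.15 × 3.29 = 1.3 points, against an SE of 3.29 points.

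**The case against.** The strongest reply is that nothing here is an error. The crude interval is valid under randomization, and the comparison is secondary, descriptive and outside the confirmatory testing sequence. The crude difference also equals the difference of the two group SCRs that are reported and judged against the CBER and CHMP criteria. A Mantel-Haenszel-weighted difference generally does not. Any baseline imbalance will be visible in the Day 1 HI GMTs, seroprotection rates and reverse cumulative curves. The confirmatory HI comparison already adjusts for pre-dose titer. The cut-points proposed here come from no titer distribution in the documents. All of this stands, and it is why the crude interval should remain.

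It does not remove the precision argument. Showing an imbalance in a table is not the same as accounting for it in the interval read against 10 points.

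Three stronger readings are tempting, and the documents do not support them:

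- **Chance imbalance biases the crude SCR difference.** It does not. The imbalance is part of the sampling variance that the interval already covers.
- **A fixed loss of 2 to 5 points in every strain.** That needs R² of about 0.10 to 0.15, which neither document gives. Some scenarios gain almost nothing.
- **High pre-dose titers always mean low seroconversion.** Neither document says so, and Step 5 shows a non-monotone pattern.

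**Conclusion.** The point holds as one of lost precision. Both documents specify a crude interval that ignores a baseline value which forms part of the endpoint, is collected in everyone, and is already used for the GMTs. Table 17 is correct for the planned method.

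With the four strata and the assumed titer distributions, nominal power rises by about 1 to 5 points per strain. The wider grid gives roughly 0 to 6, though it treats every titer level as a category and four strata may recover less. All these figures assume a true SCR difference of zero.

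A reader might infer that the trial's conclusion is at risk. It is not, because no confirmatory claim rests on SCR. The change is worth making because it is cheap, but it is optional.

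**What to change.** In Protocol 9.4.2 and SAP 4.3.1.1, add for each strain a 95% Miettinen-Nurminen interval for Control minus Co-Ad, stratified by that strain's Day 1 HI titer. Suitable categories are <10, 10–<40, 40–<160 and ≥160. Whatever cut-points are chosen, keep a boundary at 1:10, state the weights, and write down a fixed rule for merging sparse strata. Read the upper limit against the same 10-point reference limit.

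Report it beside the planned crude interval and state in advance which of the two is the reference. If the crude interval stays the reference, Table 17 needs no change. If the stratified one is chosen, add a note that Table 17 was computed for the crude method.

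The cost is a sentence or two in each document and a few lines of code. No participant is lost, since SCR already requires the pre-dose titer. The small downsides are that the strata must be fixed beforehand and that a footnote must explain why the weighted difference does not equal the difference of the two crude SCRs.

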9.5. Interim analyses

9.5.1. Sequence of analyses

A final analysis will be conducted once all the immunogenicity data (as clean as possible) are available for primary and secondary endpoints. This final analysis will include immunogenicity and safety data up to Visit 2 (Co-Ad group) or Visit 3 (Control group). Participants who undergo Visit 2 or Visit 3 assessments out of the allowed visit interval (see [Table 3](#) and [Table 4](#)) may be excluded from the final analysis.

An EoS analysis with all data including the data obtained until 6 months post-last dose will be performed.

9.5.2. Statistical consideration for interim analysis

Not applicable.

10. SUPPORTING DOCUMENTATION AND OPERATIONAL CONSIDERATIONS

10.1. Appendix 1: Regulatory, Ethical, and Study Oversight Considerations

10.1.1. Regulatory and ethical considerations

- This study will be conducted in accordance with the protocol and with:
 - Consensus ethical principles derived from international guidelines including the Declaration of Helsinki and Council for International Organizations of Medical Sciences International Ethical Guidelines
 - Applicable ICH Good Clinical Practice (GCP) Guidelines
 - Applicable laws and regulations
- The protocol, protocol amendments, ICF, Investigator Brochure, and other relevant documents (e.g. advertisements) must be submitted, to an IRB/IEC by the investigator for review and approval. These documents will be signed and dated by the investigator before the study is initiated.
- Any protocol amendments will require IEC/IRB approval before implementation of changes made to the study design, except for changes necessary to eliminate an immediate hazard to study participants.
- GSK will provide full details of the above procedures to the investigator, either verbally, in writing, or both.
- The investigator will be responsible for the following:
 - Providing written summaries of the status of the study to the IRB/IEC annually or more frequently in accordance with the requirements, policies, and procedures established by the IRB/EC.
 - Notifying the IRB/IEC of SAE(s) or other significant safety findings as required by IRB/IEC procedures.
 - Providing oversight of the conduct of the study at the site and adherence to requirements of 21 CFR, ICH guidelines, the IRB/IEC, European regulation 536/2014 for clinical studies (if applicable) and all other applicable local regulations.

10.1.2. Financial disclosure

Investigators and sub-investigators must provide the sponsor with full and accurate financial disclosure, as requested, to allow the sponsor to submit complete and accurate financial certification or disclosure statements to the appropriate regulatory authorities. Investigators must provide their financial interest information before initiation of the study center and again at the end of the study. Investigators are responsible for providing a financial disclosure update if their financial interests change at any point during study participation and for 1 year after completion of the study.

10.1.3. Informed consent process

The investigator or his/her representative must fully explain the nature of the study to the participant and answer all questions regarding the study.

Participants must be informed that their participation is voluntary.

Freely given and written/witnessed informed consent must be obtained from each participant and/or each participant's witness, as appropriate, prior to participation in the study.

The content of the Informed Consent Form must meet the requirements of 21 CFR 50, local regulations, ICH guidelines, Health Insurance Portability and Accountability Act requirements, where applicable, and the IRB/IEC or study center.

The medical record must include a statement that written or witnessed informed consent was obtained before the participant was enrolled in the study and the date the consent was obtained. The authorized person obtaining the informed consent must also sign the ICF.

Participants must be re-consented to the most current version of the ICF(s) or an ICF addendum during their participation in the study.

A copy of the ICF(s) must be provided to the participants.

10.1.4. Data protection

Participants will be assigned a unique identifier by the sponsor. Any participant records or datasets transferred to the sponsor will contain only the identifier. Name and any other information which would identify the participant will not be transferred.

The participants must be informed that:

- His/her personal study-related data will be used by the sponsor in accordance with local data protection law.
- His/her medical records may be examined by Clinical Quality Assurance auditors or other authorized personnel appointed by the sponsor, by appropriate IRB/IEC members, and by inspectors from regulatory authorities.

GSK will ensure protection of the personal data of the investigator and site staff which is collected within the framework of and for the purpose of the study, in accordance with the Data Privacy Notice that will be sent to the site staff.

The participants must be notified about their rights regarding the use of their personal data in accordance with the data privacy section of the ICF.

